3.4.2 Safety Endpoints

A description of safety measures is contained in Sections 8.3 and 8.4. The analysis of safety results is described in Section 3.6.2.

Safety and tolerability will be assessed by clinical review of all relevant parameters including AEs, laboratory values, vital signs, and body weight.

The a priori safety endpoint(s) of interest are: Taste related AEs (including dysgeusia, ageusia, and hypogeusia).

3.4.3 Pharmacokinetic Endpoints

Plasma pharmacokinetic parameters, C_{max} and AUC, will be estimated using the population model developed using Phase 1 and Phase 2 data.

An exploratory analysis may be conducted to understand the pharmacokinetic and efficacy relationship.

3.5 ANALYSIS POPULATIONS

3.5.1 Efficacy Analysis Populations

The Full Analysis Set (FAS) population will serve as the primary population for the analysis of efficacy data in this study. The FAS population consists of all randomized participants who have received at least one dose of double-blind study treatment and had at least one day of eDiary entry during the treatment cycle post randomization.

The modified Full Analysis Set (mFAS) population will be used as a supportive population for primary and secondary efficacy endpoints. The mFAS population consists of all randomized participants who have received at least one dose of double-blind study treatment, and had at least 10 days of eDiary entries in each of the treatment cycles post randomization.

The completer population will be used as a supportive population for primary and secondary efficacy endpoints, and will be used for the planned interim analysis. The completer population consists of all randomized participants who have completed the TRC2.

The Per-Protocol (PP) population will be used as another supportive population for primary and secondary efficacy endpoints. The PP population excludes participants from FAS due to important deviations from the protocol that may substantially affect the results of the primary/secondary efficacy endpoint(s). Potential deviations that may result in the exclusion of a participant from the Per-Protocol population include:

- Compliance with <75% of eDiary daily entries
- No daily pelvic pain scores during TRC2

For each participant, percent eDiary compliance will be calculated using the following formula:

$$\text{eDiary Compliance (\%)} = \frac{\text{Number of days with eDiary daily entries}}{\text{Number of expected days with eDiary daily entries}} \times 100$$

The number of days with eDiary daily entries (numerator) is the number of days with eDiary daily entries during overall trial period (i.e., from the date of Visit 2 to one day before the date of Visit 7/Discontinuation) and the number of expected days with eDiary daily entries (denominator) is the number of days during overall trial period (i.e., from the date of Visit 2 to one day before the date of Visit 7/Discontinuation).

The final determination on protocol deviations will be made prior to the final unblinding of the database.

3.5.2 Safety Analysis Populations

Safety Analyses will be conducted in the All Participants as Treated (APaT) population, which consists of all randomized participants who received at least one dose of study treatment. Participants will be included in the treatment group corresponding to the study treatment they actually received for the analysis of safety data using the APaT population. This will be the treatment group to which they are randomized except for participants who take incorrect study treatment for the entire treatment period; such participants will be included in the treatment group corresponding to the study treatment actually received.

At least one laboratory, vital sign, weight, or height measurement obtained subsequent to at least one dose of study treatment is required for inclusion in the analysis of the respective safety parameter. To assess change from baseline, a baseline measurement is also required.

The evaluable PK population for PK data analysis is defined as all participants with one measurable PK sample.

3.6 STATISTICAL METHODS

This section describes the statistical methods that address the primary and secondary objectives. Methods related to exploratory objectives will be described in Section 3.6.1.

3.6.1 Statistical Methods for Efficacy Analyses

This section describes the statistical methods that address the primary and secondary objectives. The primary analysis will be based on the FAS population, and supportive analyses will be based on the mFAS, Completer population and PP population.

The efficacy analyses will be performed based on the available data during 5 cycles, defined as below:

- Screening Cycle (SC):
 - Starts the first non-bleeding day of the SC (i.e., 1 day after the last day of the menses before Visit 2) and ends the last bleeding day of SC.
- Baseline Cycle (BC) placebo run-in period:
 - Starts on the first non-bleeding day of the BC (i.e., 1 day after the last bleeding day of the SC) and ends the last bleeding day of BC.
- TRC1 after randomization:
 - Starts on Day 1 (i.e., the first study medication intervention) and ends the last bleeding day of TRC1.
- TRC2:
 - Starts on the first non-bleeding day of TRC2 (i.e., 1 day after the last bleeding day of the TRC1) and ends the last bleeding day of TRC2.
- Post-Treatment Cycle (PTC) after the participant has stopped taking study intervention:
 - Starts on the first non-bleeding day of PTC (i.e., 1 day after the last bleeding day of the TRC 2) or the day after the last dose of study medication, whichever is last and ends the last bleeding day of PTC.

Primary Efficacy Analysis

The primary efficacy endpoint is the average daily pelvic pain score during TRC2. The variable of change from baseline in the average daily pelvic pain score will be used in the analysis of the primary endpoint. The primary analysis approach will be conducted utilizing the longitudinal analysis of covariance (ANCOVA) model. In this model, the response vector consists of the change from baseline in the average daily pelvic pain scores during TRC1 and

TRC2. The model will include factors for average pelvic pain scores at baseline cycle, stratum, treatment, cycle, interaction of stratum-by-cycle, and the interaction of treatment-by-cycle as covariates. The model will use all available daily scores for calculating average pain scores during TRC1 and TRC2. The least-squares (LS) mean change from baseline at TRC2 with the associated standard errors (SEs) will be displayed for each treatment group; and the estimated treatment differences (MK-7264 – placebo) along with corresponding 95% CIs will also be presented.

Secondary Efficacy Analyses

The secondary endpoints will be analyzed in the same way as the primary endpoint.

Table 1 summarizes the key analyses strategies of the primary and secondary efficacy endpoints.

Table 1 Statistical Methods for Efficacy Endpoints

Endpoint/Variable (During TRC2)	Approach	Statistical Method	Analysis Population	Missing Data Approach
Primary				
Average daily pelvic pain scores during TRC2	P	Longitudinal ANCOVA	FAS	Observed data only
	S	Longitudinal ANCOVA	mFAS/Completer Population/PP	Observed data only
	S	Longitudinal ANCOVA	FAS	Jump to reference imputation
Secondary				
Average daily cyclic pelvic pain scores during TRC2	P	Longitudinal ANCOVA	FAS	Observed data only
	S	Longitudinal ANCOVA	mFAS/Completer Population/PP	Observed data only
	S	Longitudinal ANCOVA	FAS	Jump to reference imputation
Average daily non-cyclic pelvic pain scores during TRC2	P	Longitudinal ANCOVA	FAS	Observed data only
	S	Longitudinal ANCOVA	mFAS/Completer Population/PP	Observed data only
	S	Longitudinal ANCOVA	FAS	Jump to reference imputation
ANCOVA = Analysis of covariance; FAS = Full Analysis Set; mFAS=modified Full Analysis Set; PP = Per Protocol P = Primary; S = Supportive.				

Exploratory Efficacy Analyses

- For the continuous endpoints for the exploratory objectives, similar statistical approaches will be used as described above for the primary endpoint. Average daily use of naproxen sodium rescue medication in terms of number of tablets taken for daily pelvic pain (cyclic and non-cyclic, combined and separately) as compared to baseline during TRC2:

From the longitudinal ANCOVA model, the response vector consists of the change from baseline in the average daily use of naproxen sodium rescue medication during TRC1 and TRC2. The model will include factors for average daily use of naproxen sodium rescue medication at baseline cycle, stratum, treatment, cycle, interaction of stratum-by-cycle, and the interaction of treatment-by-cycle as covariates.

- Average daily pelvic pain scores (cyclic and non-cyclic, combined and separately) as compared to the Screening Cycle during PTC:

From the longitudinal ANCOVA model, the response vector consists of the change from screening cycle in the average daily pelvic pain scores during BC, TRC1, TRC2, and PTC. The model will include factors for average pelvic pain scores at screening cycle, stratum, treatment, cycle, interaction of stratum-by-cycle, and the interaction of treatment-by-cycle as covariates. The LS mean (SEs, and 95% CIs) will be presented.

- Average daily pelvic pain scores (cyclic and non-cyclic, combined and separately) as compared to baseline during TRC1:

The average daily pelvic pain score during TRC1 will be analyzed from the same model (including response vector and covariates) for the primary endpoint, and the LS mean (SEs, and 95% CIs) will be presented in the same way.

For the proportions in the following exploratory endpoints, they will be analyzed by logistic-regression models comparing MK-7264 with placebo, including average pelvic pain scores at baseline cycle, stratum, treatment, cycle, interaction of stratum-by-cycle, and the interaction of treatment-by-cycle as covariates.

- Proportion of participants with at least 1-point (2, or 3) reduction in average daily pelvic pain score (cyclic and non-cyclic, combined and separately) as compared to baseline during TRC2.
- Proportion of participants with at least 1-point (2, or 3) reduction in average daily pelvic pain score (cyclic and non-cyclic, combined and separately) as compared to baseline during TRC2, and no increase in the average daily use of rescue medication by number of tablets.
- Proportion of participants with at least 1-point (2, or 3) reduction in average daily pelvic pain score (cyclic and non-cyclic, combined and separately) as compared to baseline

during TRC2, no increase in the average daily use of rescue medication by number of tablets, and no use of concomitant pain medication.

- Proportion of participants with at least 1-point (2, or 3) reduction in average daily pelvic pain score (cyclic and non-cyclic, combined and separately) as compared to baseline during TRC2, no increase in the average daily use of rescue medication by number of tablets, and no use of concomitant pain medication for ERP.

The following PRO exploratory endpoints will be analyzed using available data.

- Endometriosis Health Profile (EHP)-5:

The EHP-5 is an endometriosis-specific questionnaire to assess the participant's health-related quality of life. Participants will respond by selecting one of these five categorical responses- "never", "rarely", "sometimes", "often", "always"- at the beginning of the run-in period (Visit 3) and at the end of TRC 2 (Visit 6) on 5 items from the core questionnaire. The EHP-5 responses will be summarized in terms of frequencies and percentages in the cross-classification table for each of 5 items.

- The Patient's Global Impression of Change (PGIC) ratings:

The PGIC is a 7-point scale collecting a participant's rating of overall change in her ERP relative to her condition before initiation of the treatment. Participants rate their change as "much better", "better", "a little better", "the same," "a little worse", "worse", or "much worse". Proportion of subjects with improvements (either "much better" or "better" or "a little better" on the PGIC scale) at TRC2 will be analyzed using the stratified Miettinen and Nurminen method (1985) [1].

- Impact score of pelvic pain:

Fraction of days with no impact (score=0) of endometriosis-related pain (ERP) during BC and TRC2 will be summarized on each of work/school, physical activities, leisure/social activities, and sleep items.

Additionally, change from baseline in average daily pelvic pain score (cyclic and non-cyclic, combined and separately) during TRC2 on days with rescue medication versus days without use rescue medication will also be summarized.

Handling of Missing Data

Sensitivity analyses will be conducted to incorporate methods for handling missing data (i.e., no eDiary entry for either TRC1 or TRC2). The missing data will be imputed based on jump-to-reference method, that is, the missing scores after dropout time in treatment group will be imputed from the placebo group.

The longitudinal data analysis (LDA) method assumes that data are missing at random (MAR). In this study, it is expected that missing at random and missing completely at random (MAR/MCAR) mechanisms will underlie most of the missingness, and the proportion of data missing not at random (MNAR), driven solely by unobserved values of the

study endpoints, will be small. The multiple imputation (MI) approach will be used to assess the robustness of the primary analysis approaches.

Jump-to-reference (J2R) Multiple-imputation Analysis

J2R imputation falls under the category of pattern mixture models known as reference-based imputation (RBI). The RBI approach uses different imputation models for missing data in different treatment groups. In J2R, missing data in the control group are imputed under the MAR assumption, while missing data in the treatment groups are imputed under a MNAR assumption using the control group profile for time points after withdrawal.

The following steps will be used to implement the J2R multiple-imputation analysis.

- 1) A parameter-estimation model is fitted using PROC MCMC. All of the covariates included in the primary analysis will be used for the parameter-estimation model. For the MCMC procedure, an initial random seed = 72642730 will be used. N = 500 sets pseudo-independent samples of the model parameters will be drawn from the joint posterior distribution.
- 2) The imputation model is built, where, for each pattern of withdrawal, a predicted value model is created using the parameters estimated in Step 1. The random seed for the imputations is 72642730. For subjects in the control (reference) group, the predicted means are calculated under MAR assumption; for subjects in the other treatment arm, the predicted means are calculated under MNAR using the jump-to-reference approach, that is, the mean profile is based on the same treatment arm before withdrawal and ‘jumps’ to the mean profile based on the reference arm after withdrawal. A complete dataset will be generated using the imputation model for each set of the N = 500 parameters obtained in Step 1.
- 3) For each of the imputed complete datasets, an ANCOVA model will be used for the change from baseline values at last time point. The model will include the same covariates as in the primary analysis model. The treatment difference across the 500 datasets will then be combined using PROC MIANALYZE, i.e., using Rubin’s rule for multiple imputation (Rubin, 1987) to provide the final results.

To get correct the variance for the jump-to-reference imputation method, a pattern mixture model approximation will also be used. Based on the definition, the jump-to-reference imputation will have a mean treatment difference of zero between treatment and control for those who dropped out in the treatment arm. Therefore, the overall mean treatment difference for jump-to-reference becomes

$$\theta^{J2R} = (\pi_t \mu_t^d + (1 - \pi_t) \mu_t^p) - \mu_t^p = \pi_t (\mu_t^d - \mu_t^p)$$

where π_t is the proportion of completers (i.e., subjects with non-missing response at t) in the drug group, t is the last time point, and μ_t^d and μ_t^p are the mean effects for drug and control, respectively. It can be estimated from the primary analysis model as $\hat{\theta}^{J2R} = \hat{\pi}_t (\hat{\mu}_t^d - \hat{\mu}_t^p)$.

The variance can be approximated by,

$$\text{var}(\hat{\theta}^{J2R}) = \hat{\pi}_t^2 \text{var}(\hat{\mu}_t^d - \hat{\mu}_t^p) + (\hat{\mu}_t^d - \hat{\mu}_t^p)^2 \hat{\pi}_t (1 - \hat{\pi}_t) / n$$

where n is sample size in the drug treatment arm. The first term can be estimated from the primary analysis model.

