1.3 Schedule of Activities (SoA)

Study Period	Screening		Placebo Run-in	Treatment Period			Post Treatment Period			Notes
	Visit 1	Visit 2		Visit 3	Visit 4	Visit 5	Visit 6	Telephone Contact	Visit 7	
Visit Number	Visit 1	Visit 2	Visit 3	Visit 4	Visit 5	Visit 6	Telephone Contact	Visit 7	DC	End of menses = end of any visible menstrual flow Asterisk (*) in DC column indicates procedures not required if DC after V6. See Section 8.10.5 for procedures performed after DC.
Scheduled Day	~1 week before menses	Day after end of menses Begin SC	Day after SC menses ends Begin BC	Day after BC menses ends Day1/ Randomization	Day after TRC1 menses ends	Day after TRC2 menses ends	2 weeks after last dose of study intervention	Day after PTC menses ends		
Scheduling Window	-14 days	+3 days	+3 days	+3 days	+3 days	+3 days	+3 days	+3 days		
Administrative and General Procedures										
Written Informed Consent	X									Screening may occur over several days after consent is signed.
Informed Consent for Future Biomedical Research (FBR)	X									Participant may participate in main study without participating in FBR.
Assignment of Screening Number	X									
Participant Identification Card	X									At the time of randomization, site will add randomization number to participant identification card
Inclusion/Exclusion Criteria	X	X	X	X						Evaluate entry criteria at each visit, See Section 5.
Medical History	X									
Gynecological History	X									
Prior/Concomitant Medications	X	X	X	X	X	X	X	X	X	
Rescue Medication (Naproxen sodium) Dispensing and Instructions for Use		X	X	X	X	X				

Study Period	Screening		Placebo Run-in	Treatment Period			Post Treatment Period			Notes
	Visit 1	Visit 2		Visit 3	Visit 4	Visit 5	Visit 6	Telephone Contact	Visit 7	
Visit Number	Visit 1	Visit 2	Visit 3	Visit 4	Visit 5	Visit 6	Telephone Contact	Visit 7	DC	End of menses = end of any visible menstrual flow Asterisk (*) in DC column indicates procedures not required if DC after V6. See Section 8.10.5 for procedures performed after DC.
Rescue Medication (Naproxen sodium) Accountability			X	X	X	X		X	X	
Home Urine Pregnancy Test (UPT) Dispensing		X								If any menstrual cycle is 2 weeks later than expected, participant must perform UPT and contact clinic to schedule visit as soon as possible. Sponsor must be consulted. Additional UPT can be dispensed as needed.
Treatment Randomization				X						
Placebo Dispensing (For Run-In)			X							

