6.5 Concomitant Therapy

Medications specifically prohibited in the exclusion criteria are not allowed from the time specified for each medication in [Table 1](#) (Section 5.2) until early discontinuation or end of the post-treatment period. If there is a clinical indication for any medication or vaccination specifically prohibited, discontinuation from study intervention may be required. The investigator should discuss any questions regarding this with the Sponsor Clinical Director. The final decision on any supportive therapy rests with the investigator and/or the participant's primary physician. However, the decision to continue the participant on study intervention requires the mutual agreement of the investigator, the Sponsor, and the participant.

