6.5.1 Rescue Medications and Supportive Care

Naproxen sodium 275 mg tablets will be provided to participants for use as rescue medication for ERP from Visit 2 until early discontinuation or last study visit. Since the maximum appropriate dose varies by region, the dose of naproxen sodium will be based on investigational site's recommendation and the local guidance.

Participants will be instructed that they should not take pain medications other than site dispensed naproxen sodium for ERP during the study, and that naproxen sodium is to be used only as a rescue medication for ERP, not prophylactically or routinely.

The naproxen sodium tablets provided as rescue medication should not be used for the treatment of conditions other than ERP during the study. Participants must return all remaining naproxen sodium at each study visit, or discontinuation visit.

Note: Short term use (ie, ≤ 3 days) of other non-opioid pain medications for acute conditions (other than ERP) is permitted. However, the investigator should caution the participants on the use of other NSAIDs on the same day that the participant uses the naproxen sodium rescue medication.

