8.10.5 Discontinued Participants Continuing to be Monitored in the Study

If a participant is discontinued from the study intervention early, the Discontinuation Visit assessments are to be performed as indicated in the SoA.

It is intended that all randomized participants should be followed through completion of the study, regardless of premature discontinuation of treatment, unless the participant withdraws consent from any study follow-up. Thus, participants who discontinue from study intervention before completion of the study should continue to be monitored after the Discontinuation Visit to obtain relevant information through the end of the study.

After the Discontinuation Visit, a telephone contact will be conducted 14 days following cessation of double-blind study intervention during which all reportable safety events as outlined in Section 8.4, [Table 3](#) will be collected. After the 14 day telephone contact, only drug-related SAEs will be collected; in addition, if the investigator becomes aware of any AEs (serious or non-serious) assessed as related to the rescue medication (naproxen sodium), they must be reported to the Sponsor.

Study site visits (or telephone contacts if scheduling of site visits is not possible) should occur at timepoints that correspond to each remaining study visit on the SoA. Only safety events as specified in the paragraph above and concomitant medication information will be collected at these visits. In addition, participants will be asked to continue to provide daily eDiary entries after discontinuation of study intervention; however, if a participant does not agree to continue using the eDiary, she will still be followed for collection of safety events as specified above and concomitant medication information.

Concomitant therapies specifically prohibited (see [Table 1](#)) while the participant was on study intervention are no longer prohibited after discontinuation of study intervention.

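### Diary days after naproxen supply ends are scored as zero rescue tablets and so count as reduced rescue use (minor; exploratory rescue endpoints only)

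*Combined protocol and SAP*

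**What the plan says.** **Supply.** Protocol 6.5.1 provides naproxen "for use as rescue medication for ERP from Visit 2 until early discontinuation or last study visit" and requires leftover tablets to be handed back at each visit, including the discontinuation visit. Section 8.10.5 triggers that visit when study drug is stopped early. Section 6.5 uses the same term: prohibited medications stay barred "until early discontinuation or end of the post-treatment period", and 8.10.5 says that prohibited therapies "are no longer prohibited after discontinuation of study intervention". Early discontinuation here therefore means stopping study drug. In the Schedule of Activities (1.3), the row "Rescue Medication (Naproxen sodium) Dispensing and Instructions for Use" is marked for Visits 2 to 6 and is blank under DC, while the rescue accountability row is marked there.

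**Diary.** Section 8.10.5 states that "participants will be asked to continue to provide daily eDiary entries after discontinuation of study intervention". The rescue item (8.2.1.4) asks only about naproxen from the site and how many tablets were taken. Any other analgesic goes into a separate item (8.2.1.5).

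**Analysis.** sSAP 3.6.1 says "The efficacy analyses will be performed based on the available data during 5 cycles". Treatment Cycle 2 "ends the last bleeding day of TRC2". For the efficacy cycles, the last dose appears only in the start rule for the post-treatment cycle, so nothing cuts TRC1 or TRC2 at last dose or at end of supply. For rescue use, "the response vector consists of the change from baseline in the average daily use of naproxen sodium rescue medication during TRC1 and TRC2". Three responder composites combine a pain reduction with no rise in rescue tablets. One has no further analgesic condition, one also requires no other pain medication, and one also requires no other pain medication for endometriosis-related pain.

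**The concern.** Protocol 4.2.1.1 treats rescue use, and its difference between arms, as a sign of how well treatment controls pain. A zero recorded because the woman has no tablets says nothing about pain control. She may have gone back to her own analgesic, which 8.10.5 now permits. Her rescue count is still zero and the model reads it as improvement.

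The error favours whichever arm has more women who stop study drug and keep the diary. That is plausibly MK-7264: protocol 4.3.3 reports that 10% stopped for taste effects at 50 mg bid in a 12-week cough study. No planned analysis would expose it, because the supportive populations and the jump-to-reference analysis cover only the primary and secondary endpoints (sSAP 3.5.1 and Table 1).

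**Working it through.** **Plan's own figure.** The documents give no figure for rescue use. The stated 84% power for the primary endpoint reproduces (84.1% with 70 per arm, difference 1, SD 2, two-sided 0.05), but it has no bearing here.

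**Step 1: one woman.** Assume a 28-day cycle and 2 tablets/day at baseline. The sSAP has no rule for unsupplied days, so a diary answer of no is taken as zero tablets.
- Supply ends midway through TRC2: (14 x 2 + 14 x 0)/28 - 2 = -1.0 tablets/day.
- Supply ends at the end of TRC1: 0 - 2 = -2.0 tablets/day.

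**Step 2: difference between arms.** Inputs:
- Share stopping, s: 10% on MK-7264 (borrowed from the cough study for illustration) and 2% on placebo (assumed).
- Tablets per day at baseline: 1 (assumed).
- Share of stoppers who keep the diary, r: 1, 0.5 or 0.25 (assumed). Sites need not monitor diary compliance after discontinuation (8.2.2), so the lower values are more likely.

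If supply is off for all of TRC2 and women without diary data are missing, the false fall in an arm is s x r / (1 - s x (1 - r)).

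| r | MK-7264 | Placebo | Difference (tablets/day) |
|---|---|---|---|
| 1 | 0.1000 | 0.0200 | -0.080 |
| 0.5 | 0.0526 | 0.0101 | -0.0425 |
| 0.25 | 0.0270 | 0.0051 | -0.022 |

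If supply ends halfway through TRC2 and r = 0.5: -(0.10 - 0.02) x 0.5 x 0.5 = -0.02. All values scale in proportion to tablets per day.

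**Step 3: other assumptions.** Take 15% to 20% stopping on MK-7264, 5% to 10% on placebo, all keeping the diary, 1 to 3 tablets/day, and 50% to 100% of TRC2 days unsupplied. The difference is -(difference in stop rates) x (unsupplied fraction) x (tablets/day).
- Smallest: 0.05 x 0.5 x 1 gives about -0.03 if 15% and 10% are paired. The pairings computed (15% v 5%, 20% v 5%, 20% v 10%) start at 0.10 x 0.5 x 1 = -0.05.
- Largest: 0.15 x 1 x 3 = -0.45.
- Equal stop rates, such as 15% in both arms: 0.

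**Step 4: the rescue-only composite.** Assume 40% of diary-keeping stoppers have the 1-point pain reduction. With the Step 2 denominators, if all of them would otherwise have failed on rescue use:
- r = 1: 0.080 x 0.40 = 3.2 percentage points.
- r = 0.5: 0.0425 x 0.40 = 1.7 points.

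If only 30% of them would otherwise have shown a rise, these become 0.96 and 0.51 points. The other two composites already fail a woman who replaces naproxen with another analgesic for endometriosis-related pain.

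**Step 5: why dropping the zeros is not enough.** Each cycle ends with menses, so the days before supply ends are mostly non-bleeding days. Assume 28 days, 5 bleeding days at 2 tablets, a cycle mean of 1, hence (28 - 10)/23 = 0.783 on non-bleeding days. True use is unchanged and supply ends after day 14.
- As planned: 14 x 0.783/28 - 1 = -0.61.
- Supplied days only, against the whole baseline cycle: 0.783 - 1 = -0.22 (-0.11 to -0.43 for 1.5 to 3 tablets on bleeding days).
- Supplied days against baseline non-bleeding days: 0.783 - 0.783 = 0.

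**The case against.** The case against acting has several parts. The zero is a true count of site-supplied tablets. The endpoints are exploratory in a Phase 2a trial and no stated decision rule depends on them. Two of the three composites largely protect themselves, and the third still requires a pain reduction. The size rests on assumed inputs: the 10% comes from another indication, a slightly higher dose and a longer study, and no SD for tablet use is given against which to judge the result. All of that stands, and it is why the point is minor. It does not rescue the zero as a measure of pain control, which is the use 4.2.1.1 makes of it.

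Two stronger readings are tempting, and the documents support neither.

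- A reader might infer that the protocol is silent or contradictory on supply. Table 2 lists naproxen for Visits 2 to 7, 8.1.7 dispenses it at Visits 2 to 6, and 7.1 asks women off study drug to complete the scheduled visits and procedures. Table 2 and 8.1.7 are general schedules; Table 2 lists MK-7264 for Visits 4 to 6 in the same way, and nobody reads that as dosing after discontinuation. Section 7.1 defers to 8.10.5, which limits later visits to safety events and concomitant medication, with diary entries continuing. With the return rule in 6.5.1, supply ends. Aligning the wording is editorial.
- A reader might infer that the primary result is biased. Zero-tablet scoring does not enter any pain score. Pain scores recorded after naproxen ends do enter the FAS average, but as real observations.

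**Conclusion.** The point holds as a minor gap in the sSAP. Followed as written, the plan scores days without supply as zero rescue tablets. Those days count as reduced use in the rescue-use model and as no rise in one composite. They also fall on the without-rescue side of the planned descriptive summary of pain by rescue use.

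The size cannot be fixed from the documents. It is about -0.02 to -0.08 tablets/day with 10% v 2% stopping and 1 tablet/day, and up to -0.45 under the heavier assumptions in Step 3. The composite shift is roughly 0.5 to 3 percentage points under the assumptions in Step 4, which is an illustration and not a bound. If stopping, its timing, tablet use and diary retention are equal across arms, the arm difference is zero. The direction in favour of MK-7264 is plausible but not established.

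**What to change.** Add a short paragraph to sSAP 3.6.1:

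1. For rescue use, days after the discontinuation visit are missing, not zero. That visit is the right cut, and not the last dose, because tablets are handed back there.
2. Compare the remaining days with the same phase (bleeding or non-bleeding) of the baseline cycle. The plan already analyses cyclic and non-cyclic use separately. For the combined value, set the cycle to missing if supply ended before that cycle's menses.
3. In the composites, unsupplied days do not count towards the condition that rescue use has not risen. Treating a woman without a usable TRC2 rescue value as a non-responder is one option. It penalises the arm with more stoppers, so the choice should be stated before unblinding.

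Leave the primary and secondary pain-score analyses unchanged. As an editorial tidy-up, 6.5.1 could name study intervention explicitly, and Table 2, 7.1 and 8.1.7 could be aligned with it.

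The cost is one paragraph and no new data: discontinuation visits, bleeding days and tablet counts are already collected. Protocol section 9 lets exploratory methods change in the sSAP before unblinding. The downside is fewer usable rescue-use cycles for women who stop early.
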